8.3.6 Cardiovascular and death events

Cardiovascular events that meet AESI criteria should be reported as such (see [Section 8.3.8](#) for details).

8.3.7 Disease-related events and/or disease-related outcomes not qualifying as AEs or SAEs

Not applicable.

8.3.8 Adverse event of special interest

Adverse event of special interest

An AESI is an AE (serious or nonserious) of scientific and medical concern specific to the Sponsor's product or program, for which ongoing monitoring and immediate notification by the Investigator to the Sponsor is required. Such events may require further investigation in order to characterize and understand them. Adverse events of special interest may be added, modified or removed during a study by protocol amendment. The following events need to be reported as AESIs:

- Pregnancy of a female participant entered in a study as well as pregnancy occurring in a female partner of a male participant entered in a study with IMP/NIMP
 - Pregnancy occurring in a female participant entered in the clinical trial or in a female partner of a male participant entered in the clinical trial. It will be qualified as an SAE only if it fulfills one of the seriousness criteria (see Appendix 3 [[Section 10.3](#)]).
 - In the event of pregnancy in a female participant, IMP should be discontinued.
 - Follow-up of the pregnancy in a female participant or in a female partner of a male participant is mandatory until the outcome has been determined (See Appendix 4 [[Section 10.4](#)]).
- Symptomatic overdose (serious or nonserious) with IMP/NIMP
 - An overdose of IMP is defined as: increase of at least 30% of the dose to be administered in the specified duration or if the dose is administered in less than half the recommended duration of administration.
 - An overdose (accidental or intentional) with the NIMP is an event suspected by the Investigator or spontaneously notified by the participant (not based on systematic pills count) and defined as at least twice the intended dose within the intended therapeutic interval, adjusted according to the tested drug.
- An elevated AST or ALT lab value that is greater than or equal to 3X the ULN and an elevated total bilirubin lab value that is greater than or equal to 2X the ULN and, at the same time, an alkaline phosphatase lab value that is less than 2X the ULN, as determined by way of protocol-specified laboratory testing or unscheduled laboratory testing*.

*Note: These criteria are based upon available regulatory guidance documents. The purpose of the criteria is to specify a threshold of abnormal hepatic tests that may require an additional evaluation for an underlying etiology. The trial site guidance for assessment and follow up of these criteria can be made available. It may also be appropriate to conduct additional evaluation for an underlying etiology in the setting of abnormalities of liver blood tests including AST, ALT, bilirubin, and alkaline phosphatase that do not meet the criteria noted

above. In these cases, the decision to proceed with additional evaluation will be made through consultation between the study investigators and the Sponsor.

- Other project-specific AESIs
 - IRR Grade ≥ 2
 - CRS Grade ≥ 2
 - ICANS of any grade
 - VLS of any grade
 - Any immune-related AE Grade ≥ 3
 - Arrhythmia Grade ≥ 3

8.3.9 Guidelines for reporting product complaints

Any defect in the IMP/NIMP must be reported as soon as possible by the Investigator to the monitoring team that will complete a product complaint form within required timelines.

Appropriate information (eg, samples, labels or documents like pictures or photocopies) related to product identification and to the potential deficiencies may need to be gathered. The Investigator will assess whether or not the quality issue has to be reported together with an AE or SAE.

8.4 PHARMACOKINETICS

[figure not shown]
The sampling time-points for PK and ADA for/against SAR444245 and/or other IMPs may be updated during the course of the study based on the updated knowledge of drug behavior upon notification from the Sponsor.

Instructions for the collection and handling of biological samples will be provided by the Sponsor in the laboratory manual. The actual date and time (24-hour clock time) of each sample will be recorded while for samples to be collected at time of biomarker sampling, no specific time on the given day is necessary.

[figure not shown]
Instructions on the collection, processing, storage, and shipment of samples will be provided in the laboratory manual. Sample analysis will be performed at a laboratory designated by the Sponsor.

[figure not shown]
Samples collected for analyses of SAR444245 concentration may also be used to evaluate safety or efficacy aspects related to concerns arising during or after the study and any remaining plasma/serum volume may also be used for further exploratory analysis if deemed relevant.

8.5 GENETICS AND/OR PHARMACOGENOMICS

8.6 BIOMARKERS

8.7 IMMUNOGENICITY ASSESSMENTS

The sampling time points for ADAs may be reduced or increased during the course of the study based on the updated knowledge of drug behavior and its immunogenicity, upon notification from the Sponsor.

Samples for the immunogenicity assessment of SAR444245 will be collected according to the PK flowcharts in the individual substudy. Instructions for the collection and handling of biological samples will be provided by the Sponsor. Sample analysis will be performed at a laboratory designated by the Sponsor.

[figure not shown]
Samples will be screened and then confirmed for anti-drug antibodies and the titer of confirmed positive samples will be reported. Additional analyses may be performed to further characterize the immunogenicity of SAR444245.

[figure not shown]
Anti-drug antibody (ADA) samples remaining after determination of immunogenicity may be kept for possible exploratory analysis of biomarkers. The exploratory data will not be included in the study report but will be kept on file.

8.8 HEALTH ECONOMICS

No health economics data will be collected.

8.9 USE OF BIOLOGICAL SAMPLES AND DATA FOR FUTURE RESEARCH

9 STATISTICAL CONSIDERATIONS

Please refer to the individual substudy protocols for additional statistical considerations.

9.1 STATISTICAL HYPOTHESES

All cohorts of the study are designed to obtain antitumor activity, safety, PK, pharmacodynamic (PDy), and immunogenicity data on SAR444245 administered either in monotherapy or in combination.

The study is designed to assess clinical benefit of SAR444245 with or without other anticancer therapies in adults and adolescents with relapsed or refractory B cell lymphoma. As this study is not intended to explicitly test a hypothesis, calculations of power and Type I error were not considered in the study design. No formal testing procedure is going to be considered.

9.2 SAMPLE SIZE DETERMINATION

The study will start with a safety run-in with 6-10 participants from each cohort. Participants who are enrolled in the safety run-in and treated at the confirmed safe dose will be included in the total number of participants from their given cohort.

Sample size:

Number of participants to be enrolled in each cohort is described in the substudies.

9.3 POPULATIONS FOR ANALYSES

The following populations for analyses are defined:

Table 5 - Populations for analyses

Population	Description
Exposed	Exposed population will include all participants who have given their informed consent and received at least one dose (even incomplete) of IMP (SAR444245 or other anticancer therapies).
Efficacy	Efficacy population will include all participants from the exposed population with at least one evaluable post-baseline tumor assessment or who permanently discontinued study treatment.
DLT-evaluable	DLT-evaluable population will include all participants in safety run-in part who have been treated and observed for DLT observation period (defined in the individual substudy). Any participants who have experienced a DLT during DLT observation period will also be DLT-evaluable.
Pharmacokinetic (PK)	The PK population will include all participants from the exposed population with at least 1 PK concentration available after the first dose of study intervention.
PDy	The PDy population will include all participants from the exposed population with at least 1 PDy (biomarker) parameter assessed after the first dose of study intervention.

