9.4.1 General considerations

This study is not intended to explicitly test a hypothesis, and 90% confidence interval (CI) will be provided for primary and secondary efficacy endpoints for descriptive purpose only.

All efficacy analyses will be performed on the efficacy population and analyzed by cohort. Objective response rate (ORR), CRR as well as all other efficacy variables will be derived using local radiologist's/Investigator's assessment for all cohorts according to Lugano response criteria 2014.

All safety analyses will be performed on the exposed population by cohort, by dose (if applicable) and overall (if applicable). A baseline value will be defined as the latest value or measurement taken up to the first administration of the IMP.

The analysis period will be divided into 3 segments:

- The **pre-treatment period** is defined as the time from when the participants give informed consent to the first administration of the IMP.
- The **on-treatment period** (ie, treatment-emergent period) is defined as the time from the first administration of IMP up to 30 days after the last administration of IMP.
- The **post-treatment period** is defined as the time from the 31 days after the last administration of IMP.

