4 STUDY DESIGN

4.1 OVERALL DESIGN

This substudy will include approximately 25 participants with diffuse large B cell lymphoma (DLBCL) who have received at least 2 lines of systemic therapy and have either stable or progressive disease 1-3 months after receiving a Health Authority approved CAR-T therapy. The substudy will assess SAR444245 monotherapy as at least 3rd line of therapy.

Please refer to the master protocol for a full description of the study design, and for details applicable to all therapy cohorts.

A graphical presentation of the study schema is shown in [Figure 1](#).

The dose-limiting toxicity (DLT) observation period is 28 days for Cohort C1. The maximum cycles allowed in this substudy for Cohort C1 are 52 cycles.

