6.5.2 Dose delay and dose omission

Within a cycle, the treatment windows are:

- For the Q2W administration, the C_{n+1} (± 2 days), dose is deemed to have been delayed if the treatment is ≥ 3 days beyond the theoretical day of treatment.
- The reason for the dose delay will be captured. If the reason for the dose delay is an adverse event, the participant will receive the next infusion after recovery of the AE as described in [Section 6.5.2](#) and [Section 6.5.3](#)

Participants may have dose omission if an AE occurs and does not recover according to following rules:

- If an AE occurs and the participant does not recover on the day of planned infusion or within the following 2 days, infusion of SAR444245 may be omitted for participants.
- In case of consecutive dose omissions/delay for the recovery of AE, the following rules should be followed for restart or discontinuation of the treatment:
 - Dose delay (cycle delay) up to 9 days, it is per Investigator's decision to restart the study treatment.
 - After dose delay of >9 days and ≤ 84 days, it is per Investigator's decision to restart the study treatment, if a clear benefit from treatment is observed and after consultation with the Sponsor.
 - Treatment must be permanently discontinued if the delay is longer than 84 days.

Cycle may be delayed for situations other than TEAEs such as medical / surgical events or logistical reasons not related to study therapy. Participants should be placed back on study therapy within 14 days of the scheduled delay, unless otherwise discussed with the Sponsor (for example for national or regional emergencies). The reason for this delay should be documented in the participant's study record.

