2 ANALYSIS POPULATIONS

The following populations for analyses are defined. Unless otherwise specified, these populations will be applicable for both safety run-in and core phase parts. The participants included in the safety run-in part, if fulfilling the inclusion criteria of the core phase part and if the planned dose and dosing schedule are the same as in core phase will be included in the analyses of core phase.

Table 4 - Populations for analyses

Population	Description
Screened	All participants who have been given the informed consent form.
Enrolled	All participants who have given their informed consent and have been allocated to an intervention (by IRT) regardless of whether the intervention was received or not.
Exposed	All participants who have given their informed consent and received at least one dose (even incomplete) of IMP (SAR444245 or pembrolizumab).
Population without trial impact (disruption) due to COVID-19	All exposed participants: 
without any critical or major deviation related to COVID-19and who did not permanently discontinue treatment due to COVID-19and who did not permanently discontinue study due to COVID-19.
Efficacy	All participants from the exposed population with at least one evaluable post-baseline tumor assessment or who permanently discontinued study treatment.
DLT-evaluable ^a	All exposed participants in safety run-in part who have been treated and observed for DLT observation period (defined in the individual substudy). Any participants who have experienced a DLT during DLT observation period will also be DLT-evaluable.
Response evaluable	All participants from the efficacy population with at least one baseline and one evaluable post-baseline tumor assessments. Participants who died from disease progression before any TA will also be response-evaluable.
Pharmacokinetic (PK)	All participants from the exposed population with at least 1 PK concentration available after the first dose of study intervention.
ADA	All participants from exposed population with at least 1 ADA result (positive, negative or inconclusive) after the first dose of study intervention.
Pharmacodynamics (PDy)	All participants from the exposed population with at least 1 PDy (biomarker) parameter assessed after the first dose of study intervention.

^a The dose-limiting toxicity (DLT) observation period is 21 days for Cohort A, and 28 days for Cohort C1.

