3 STATISTICAL ANALYSES

3.1 GENERAL CONSIDERATIONS

In general, continuous data will be summarized using the number of observations available, mean, standard deviation (SD), median, minimum, and maximum. Categorical and ordinal data will be summarized using the count and percentage of participants.

The baseline value is defined as the last available value before the first administration of any of the two IMPs (SAR444245 or pembrolizumab). For participants enrolled but not treated, the baseline value is defined as the last available value before enrollment.

Unless otherwise specified, analyses will be performed by cohort, by dose level (if applicable) and overall. Participants enrolled in the safety run-in part and treated at the RP2D will be included in the analyses of the core part.

All efficacy analyses will be performed on the efficacy population. Complete response rate (CRR, for cohort A) and objective response rate (ORR, for cohort C1), as well as all other response-related efficacy endpoints will be derived using the Investigator's assessment per Lugano response criteria 2014 for all cohorts.

All safety analyses will be performed on the exposed population.

Central imaging may be done retrospectively if significant activity is observed (See [Section 3.2.3](#) for sensitivity analysis).

Confidence intervals will be two-sided 90% CI for efficacy analyses. CI will be used for descriptive purposes only, without inference.

The BOR is defined as the best overall response observed from the date of first IMP until disease progression, death, cut-off date or initiation of subsequent anti-cancer therapy, whichever occurs first.

Analysis period

The analysis period will be divided into 3 segments:

- The **pre-treatment period** is defined as the time from when the participants give informed consent to the first administration of the IMP.
- The **on-treatment period** (i.e., treatment-emergent (TE) period) is defined as the time from the first administration of IMP up to 30 days after the last administration of IMP.
- The **post-treatment period** is defined as the time from the end of the on-treatment, ie. 31 days after the last administration of IMP.

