3.6 SAFETY ANALYSES

All safety analyses will be performed on the exposed population as defined in [Section 2](#).

The analysis of the safety variables will be descriptive, and no testing is planned.

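### DLT-evaluable status needs no minimum SAR444245 exposure, so an under-dosed run-in participant counts as a full DLT-free observation; separately, DLT incidence has no SAP summary and, read literally, the wrong denominator

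*Protocol*

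**What the plan says.** **Who is DLT-evaluable.** Protocol Section 9.3, Table 5, takes "all participants in safety run-in part who have been treated and observed for DLT observation period" and adds anyone who had a DLT in the window. Master protocol Section 4.1 gives the same rule. SAP Section 2, Table 4, has "All exposed participants in safety run-in part who have been treated and observed for DLT observation period". Exposed, in that table, means having "received at least one dose (even incomplete) of IMP (SAR444245 or pembrolizumab").

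**How the set is used.** Master protocol Section 4.1 sends a cohort to the Study Board once at least 6 participants are DLT-evaluable. The columns of the mTPI-2 table (Table 2) count DLT-evaluable participants.

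**How under-dosing can arise.**
- Both substudies: a Grade 2 SAR444245 infusion reaction calls for interrupting the infusion (Section 6.5.4.1).
- Cohort C1: "The dose-limiting toxicity (DLT) observation period is 28 days for Cohort C1" (Substudy 03, Section 4.1), and dosing is every 14 days, so two doses are planned in the window. Under Section 6.5.2, after an unresolved adverse event, "infusion of SAR444245 may be omitted for participants".
- Cohort A: after a Grade 3 or 4 pembrolizumab reaction SAR444245 is delayed, and Table 3 of Substudy 01 ends study drug permanently (Section 6.5.4.1).

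**Reporting.** DLT incidence is a secondary endpoint (SAP Section 1.2). SAP Section 3.1 states "All safety analyses will be performed on the exposed population", and Section 3.6 repeats it. Protocol Section 9.4.1 has "All safety analyses will be performed on the exposed population by cohort, by dose (if applicable) and overall (if applicable"). None of the three makes an exception for DLTs, and SAP Section 3.6 contains no DLT summary.

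**The concern.** There are two separate problems.

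1. **Dose decision.** The mTPI-2 rule treats every counted participant as one full trial of the dose under test. A participant who received part of the planned SAR444245, or none, and had no DLT adds to the denominator with less than a full chance of adding to the numerator. The error runs one way, towards continuing at 24 µg/kg. In Cohort A an event obviously unrelated to SAR444245 is not a DLT. So a participant stopped by a pembrolizumab reaction can be kept out of the numerator and still count in the denominator. Extra enrolment under Section 4.1 is triggered only when fewer than 6 are evaluable, and this definition does not trigger it for under-dosed participants.

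2. **Reporting.** SAP Section 3.3 sends safety endpoints to Section 3.6, whose only stated population is the exposed set. Run-in participants are pooled with the core part (SAP Sections 2 and 3.1). Taken literally, run-in DLTs would be divided by a group most of whom were never assessed for DLT.

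**Working it through.** **Step 1: reproduce Table 2.** Inputs from master protocol Section 4.1: target 0.30, equivalence interval (0.25, 0.35), and intervals (0, 0.05), (0.05, 0.15), …, (0.95, 1). The documents do not give the prior or the cut-off for DU; I assumed the standard choices, Beta(1,1) and P(p > 0.30 | data) > 0.95. With x DLTs in n, the posterior is Beta(1 + x, 1 + n − x). The unit probability mass of an interval (a, b) is [F(b) − F(a)] / (b − a), and the interval with the largest value decides. All 65 of 65 cells match Table 2.

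**Step 2: can one participant change the decision within the reviewable range (n of at least 6)?** Yes. 3/8 = 0.375 falls in (0.35, 0.45), and Table 2 gives D. 3/9 = 0.333 falls in (0.25, 0.35), and Table 2 gives S. Adding one uninformative DLT-free participant to 3/8 moves the recommendation from de-escalate to stay.

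**Step 3: worst-case size at n = 6.** Table 2 recommends de-escalation (D or DU) at 3 or more DLTs in 6. Let m be the number adequately dosed, and assume the others cannot have a DLT. Then P(de-escalate) = P(X ≥ 3), with X ~ Binomial(m, p).

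At p = 0.40:
- m = 6: 1 − (0.6⁶ + 6·0.4·0.6⁵ + 15·0.4²·0.6⁴) = 1 − (0.0467 + 0.1866 + 0.3110) = 0.456
- m = 5: 10·0.4³·0.6² + 5·0.4⁴·0.6 + 0.4⁵ = 0.2304 + 0.0768 + 0.0102 = 0.317

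| True DLT rate | All 6 adequately dosed | One of 6 not | Two of 6 not |
|---|---|---|---|
| 10% | 1.6% | 0.9% | – |
| 20% | 9.9% | 5.8% | – |
| 30% (target) | 25.6% | 16.3% | 8.4% |
| 40% | 45.6% | 31.7% | 17.9% |
| 50% | 65.6% | 50.0% | 31.2% |

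At n = 10 with one not adequately dosed, the falls are 35.0% to 27.0%, 61.8% to 51.7% and 82.8% to 74.6% at 30%, 40% and 50%.

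**Step 4: reporting denominator.** With 25 planned per cohort, 2/6 = 33.3% becomes 2/25 = 8.0%, and 3/10 = 30.0% becomes 3/25 = 12.0%.

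**Step 5: is a DLT denominator assigned elsewhere in the SAP?** PK concentrations are assigned to the PK population (Section 3.7.1.1) and ADA results to the ADA population (Section 3.7.1.2). The DLT-evaluable population is defined in Table 4, but no analysis section uses it, and Table 8 lists no DLT row.

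**The case against.** **On the dose decision.**
- Step 3 is a worst case. A Cohort C1 participant who had a full first dose was at risk, and master protocol Section 8.2 places the expected cytokine-release events about 12 to 18 hours after first administration. A partial infusion also carries risk. This stands, so the table gives upper bounds.
- The omission rule in Substudy 03 Section 6.5.2 is driven by adverse events, and those participants should stay in the set in any case. This stands, and the fix keeps them.
- Table 2 guides the Study Board, which may depart from it and weighs all safety data, including other SAR444245 studies. A DMC trigger follows the run-in. This softens the effect but does not remove it: nothing requires that under-dosing be shown to the Board.
- The protocol's 24 µg/kg every-3-weeks data (no DLT in 11 on monotherapy, 1 in 6 with pembrolizumab, none in 5 with cetuximab; Section 4.3) suggest that the lower rows of the table may be nearer the truth, where the absolute shift is small. That bears mainly on Cohort A, because no every-2-weeks figure at this dose is given.

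**On reporting.** Table 4 defines the DLT-evaluable set and footnotes each cohort's window, so it was presumably meant for DLT summaries. That is a fair reading of intent, but no sentence says it, and three say otherwise.

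**Stronger readings that the documents do not support.**
- A reader might infer that the exposed-population rule also favours confirming 24 µg/kg. It cannot, because the Board review and Table 2 use DLT-evaluable participants.
- A reader might cite 2/5 (D) against 2/6 (S). Five evaluable participants is below the review minimum, so that pair is not reachable.
- A reader might take participants with no SAR444245 to be possible in both cohorts. In Cohort C1 it is the only IMP. In Cohort A the route assumes that pembrolizumab is given first, which Section 6.5.4.1 implies but the redacted dosing sequence does not confirm.

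**Conclusion.** Both parts hold, with different weight.

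**Part 1 is a cheap improvement.** The definition admits under-dosed, DLT-free participants as full observations, and the bias runs towards continuing 24 µg/kg. One such participant among six lowers the chance of a de-escalation recommendation by at most 9.3 percentage points at a true rate of 30% (25.6 − 16.3), 13.9 at 40% (45.6 − 31.7) and 15.6 at 50% (65.6 − 50.0). These figures assume that the participant cannot have a DLT and that Table 2 is followed. How often under-dosing will occur is not in the documents, so no expected effect can be given.

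**Part 2 is wrong as written, and affects reporting only.** A secondary endpoint has no planned summary, and the stated default denominator does not fit it. It would be too strong to say that the sponsor plans to report 8%; that is what the text gives if applied literally.

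**What to change.** 1. **Protocol Section 9.3 and SAP Table 4** (and the matching text in master protocol Sections 1.1 and 4.1): require a participant without a DLT to have received a sponsor-specified minimum of the planned SAR444245 within the DLT window. State how partial infusions are counted and how the second Cohort C1 dose is treated. The threshold is for the sponsor to set; the documents offer none.
2. **Replacement:** replace run-in participants who fall short for reasons other than SAR444245 toxicity. Keep those whose omission or interruption was due to SAR444245 toxicity, and show their number and reasons to the Study Board.
3. **SAP Section 3.6**, with a matching exception in SAP Section 3.1 and protocol Section 9.4.1, add: *DLT incidence is summarised on the DLT-evaluable population by cohort and dose level.*

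The cost is wording and occasionally one more run-in participant. Section 4.1 already allows extra enrolment to reach six evaluable.
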